This document is a clinical investigation plan (CIP) for the AMPLATZER Duct Occluder II® Additional Sizes (ADO II AS) clinical investigation. This clinical investigation is intended to demonstrate the safety and effectiveness of St. Jude Medical's ADO II AS in subjects with a patent ductus arteriosus (PDA). This clinical investigation will be conducted under an investigational device exemption (IDE) and is intended to support market approval of the ADO II AS device in the United States and other countries. This clinical investigation is sponsored by St. Jude Medical (SJM).

This clinical investigation will be conducted in accordance with this CIP. All parties involved in the conduct of the clinical investigation will be qualified by education, training, or experience to perform their tasks and this training will be documented appropriately.

1.1 Continued Access Protocol (CAP) Enrollment

[REDACTED]

1.2 Scope and Description of CAP Enrollments

[REDACTED] pertaining only to CAP subjects are organized as sub-sections of their corresponding protocol section. These sub-sections are labeled 'for CAP Subjects' and are underlined for identification. For these subjects, the content of these sub-sections replaces the corresponding content of the associated protocol section. If sections of this protocol are not accompanied by a section specified for CAP subjects, then the original IDE section will be followed for all subjects.

[REDACTED]

2 Background and justification for clinical investigation

2.1 Disease to be treated

In the fetus, 85% of the blood bypasses the unexpanded lungs. The blood flows from the right ventricular outflow tract through the ductus arteriosus to the aorta. At birth, the increase in oxygen tension leads to inhibition of local prostaglandins and causes functional closure of the ductus, followed by anatomic closure. A patent ductus arteriosus (PDA) is a persistence of the fetal connection (ductus arteriosus) between the aorta and pulmonary artery after birth, resulting in a persistent left-to-right shunt. PDA is the most common congenital heart lesion in newborns and accounts for approximately 5 to 10% of all congenital heart defects. The incidence of a PDA is approximately 1 in 2,000 term newborns and this incidence increases to >50% in premature babies, and >80% in severely premature low birth weight infants (<1200 gm) [1]. PDA is more commonly seen in female infants, with a female-to-male ratio of 2:1 for PDA [2].

Typically the PDA will close in the first 10-18 hours of life, and anatomically, it is generally closed within six weeks [3]. PDA anatomy varies considerably both in diameter, length and configuration. Krichenko et al

[REDACTED]

provided angiographic classification of the different PDA configurations labeled as A-type through E-type, which recently has been expanded by Philip et al [4] to also include the tubular and longer F-type configuration commonly seen in premature born infants [5]. The PDA diameter refers to its narrowest segment, which is smaller than 4 mm in 78% of cases [6].

While this lesion may spontaneously resolve in some neonates, persistence, particularly in premature infants is a major health concern. The presence of a hemodynamically significant PDA in premature infants has been associated with an increased risk of developing necrotizing enterocolitis, chronic respiratory disease, pulmonary hemorrhage, intraventricular hemorrhage, and death [1, 7]. Should a baby survive the neonatal period with a significant PDA, this lesion can result in continued morbidity during infancy, which includes failure to thrive, chronic respiratory infections, and repeated hospital admissions.

Closure of PDA is indicated to restore hemodynamic status and to prevent congestive heart failure, pulmonary vascular disease, and, in the long-term, bacterial endocarditis [8]. The risk of endocarditis with small residual shunts remains unknown, although continued bacterial endocarditis prophylaxis is generally advocated as long as flow persists or a murmur can be auscultated [9].

2.2 Current Treatment Options

The current standard of care for a persistent patent ductus arteriosus (PDA) includes the following two treatment options: surgical ligation or closure with alternative devices.

Surgical Ligation

PDA was the first congenital cardiac heart disease to be conquered by surgeons. The first surgical ligation of a PDA was performed by Gross and Hubbard in 1939 [10]. Surgical ligation or ligation and division were the standard of care for persistent PDA until the advent of transcatheter closure. Today surgery remains the standard of care for PDA closure in preemies and infants with large hemodynamically significant PDAs. Although the standard of care, surgical ligation has been associated with the potential risk for significant procedural complications (pneumothorax, hypothermia, bleeding, phrenic nerve palsy, chylothorax, wound infection, vocal cord paralysis, and thoracic scoliosis [1, 7, 11, 12]), significant post-procedural clinical decline known as post-ligation syndrome [13], and poor long-term outcomes including neuro-developmental delay, retinopathy of prematurity and chronic lung disease (bronchopulmonary dysplasia) [11, 12]. Because a growing body of literature has suggested that surgical ligation of PDA in premature neonates may actually result in worse outcomes than no treatment at all a trend of permissive conservative observation of this lesion has developed, reserving surgery for only the most severe cases. Unfortunately, recent data suggests that this approach is associated with an increased risk for the development of chronic lung disease and death [15].

Transcatheter device closure

The first interventional closure of a PDA was performed by Portsmann in 1967 [14] and has emerged as the gold standard for treatment of this lesion in larger infants, children and adults [7]. Historically, transcatheter closure of a PDA has not been performed in infants and premature neonates for a variety of reasons including: fear of patient fragility; concerns regarding vascular access and arterial injury; unknown effects of intravenous contrast media; concerns regarding catheter manipulation; and most importantly, absence of a suitable PDA closure device. Recently, a growing body of clinical evidence has emerged suggesting that transcatheter closure of PDA can be performed safely and effectively in selected infants and premature newborns. The ADO II AS device has the ideal characteristics (size, shape, delivery system) for this unique population but its lack of availability in the USA has limited wide spread adaptation of this procedure.

2.3 AMPLATZER PDA Occluder

The AMPLATZER Duct Occluder II received PMA approval on August 15, 2013. [REDACTED]

[REDACTED]

[REDACTED]

[REDACTED]

[REDACTED]

[REDACTED] The AMPLATZER Duct Occluder II Additional Sizes device was designed as a line extension to ADO II to allow closure of smaller sizes of a PDA.

[REDACTED]

[REDACTED]

[REDACTED]

[REDACTED]

[REDACTED] The ADO II AS is designed to treat a PDA with a diameter ≤ 4.0 mm and a length ≥ 3.0 mm.

The ADO II AS is a self-expanding nitinol mesh occlusion device with a central waist and retention discs deployed on both ends. The central waist of the device ranges in diameter from 3 to 5 mm in 1 mm increments. The retention discs have a diameter 1, 1.25, or 1.5 mm larger than the waist diameter for the 3, 4, and 5 mm waist diameters, respectively. Each device size is available in 2, 4, or 6 mm length. The device can be delivered forward from a 4 French (4F) delivery catheter either by the aortic or venous route. The central waist is designed to fill the ductal lumen, and the retention discs are designed to deploy in the pulmonary and the aortic end of the ductus arteriosus. The ADO II AS comes pre-attached to a delivery cable. The delivery cable's distal tip is extremely flexible and has angiographically visible properties, which helps to achieve precise placement of the proximal disc during device placement and unscrewing. TorqueVue Low Profile Delivery Catheter has 4F outer diameter compatible with all 9 ADO II AS occluders.

[REDACTED]

[REDACTED]

[REDACTED]

[REDACTED]

[REDACTED]

[REDACTED]

[REDACTED] Procedural related complications associated with implanting the device in small infants may be minimized by utilizing an echocardiographic anterograde approach and avoiding invasive hemodynamic measurement and angiographic image acquisition.

Although the device is recommended for ductal diameters up to 4 mm, the largest waist diameter available is 5 mm with the retention discs only 1.5 mm larger. This leaves very little extra anchoring with this device compared to either the ADO or the ADO II, and therefore, the maximum diameter for deployment should be less than or equal to 4 mm. Tubular PDA's in young infants may stretch more easily. The small, flexible retention discs provide minimal anchoring support, meaning that the device relies heavily on constraint of the central portion for stable positioning. Careful device diameter sizing is required in larger ductal diameters to avoid embolization. The device may be implanted in ducts that are longer in length than the

length of the device, as long as the selected device diameter satisfies the specified diameter within the sizing chart.

2.4 Study Rationale (IDE and CAP)

2.4.1 Pivotal IDE Rationale

The rationale for this investigation is to offer patients a safe and effective device for closure of a small PDA (≤ 4 mm diameter) with an FDA approved device. Current treatment for smaller PDAs includes off label use of devices. Major drawbacks of current devices in terms of this unique population include: device length (too long, placing the left pulmonary artery and descending aorta at risk for obstruction), device shape (large retention disks placing the left pulmonary artery and descending aorta at risk for obstruction), and stiffness of delivery systems. Currently there is no FDA approved device for PDA closure in patients <5 kg or <6 months of age, which encompasses virtually all infants, neonates and premature neonates.

2.4.2 CAP Rationale

The rationale for the CAP is to allow current IDE study implanters to maintain their technical proficiency in ADO II AS device implantation and to allow additional implanters to gain experience with the device after enrollment completion in the pivotal cohort and while the pre-market approval (PMA) application for the ADO II AS device is being prepared and is under FDA review. Data from the CAP may be used to support post approval requirements for the ADO II AS occluder.

3 Device(s) under investigation

3.1 Identification and description of the devices under investigation

3.1.1 Identification

Figure 1: ADO II AS Device

[figure not shown]

Table 1: Identification of Devices under Investigation

Device Name	Model/Type	A mm (in)	B mm (in)	C mm (in)	Investigational or Market Released
ADO II AS Occluder	9- PDA2ASIDE-03-02	4.00 (0.157)	3.00 (0.118)	2.00 (0.079)	Investigational
ADO II AS Occluder	9- PDA2ASIDE-03-04	4.00 (0.157)	3.00 (0.118)	4.00 (0.157)	Investigational
ADO II AS Occluder	9- PDA2ASIDE-03-06	4.00 (0.157)	3.00 (0.118)	6.00 (0.236)	Investigational
ADO II AS Occluder	9- PDA2ASIDE-04-02	5.25 (0.207)	4.00 (0.157)	2.00 (0.079)	Investigational
ADO II AS Occluder	9- PDA2ASIDE-04-04	5.25 (0.207)	4.00 (0.157)	4.00 (0.157)	Investigational
ADO II AS Occluder	9- PDA2ASIDE-04-06	5.25 (0.207)	4.00 (0.157)	6.00 (0.236)	Investigational
ADO II AS Occluder	9- PDA2ASIDE-05-02	6.50 (0.256)	5.00 (0.197)	2.00 (0.079)	Investigational
ADO II AS Occluder	9- PDA2ASIDE-05-04	6.50 (0.256)	5.00 (0.197)	4.00 (0.157)	Investigational
ADO II AS Occluder	9- PDA2ASIDE-05-06	6.50 (0.256)	5.00 (0.197)	6.00 (0.236)	Investigational
AMPLATZER™ TorqVue™ LP Catheter	9-TVLPC4F90/080	Not Applicable	Not Applicable	Not Applicable	Market Released

Table 2: Device Sizing Chart for subjects >2 Kg

Measured Ductus Diameter mm (in)	Minimal Measured Ductus Length mm (in)		
	3–4 (0.118–0.157)	4.1–6 (0.161–0.236)	6.1–8 (0.240–0.315)
≤2 (≤0.079)	9-PDA2ASIDE-03-02	9- PDA2ASIDE-03-04	9- PDA2ASIDE-03-06
2.1–3 (0.083–0.118)	9- PDA2ASIDE-04-02	9- PDA2ASIDE-04-04	9- PDA2ASIDE-04-06
3.1–4 (0.122–0.157)	9- PDA2ASIDE-05-02	9- PDA2ASIDE-05-04	9- PDA2ASIDE-05-06

Table 3: Device Sizing Chart for subjects ≤2 Kg

Measured Ductus Diameter mm (in)	Minimal Measured Ductus Length mm (in)	
	3–6 (0.118–0.236)	≥6.1 (≥0.240)
≤1.5 (<0.059)	9-PDA2ASIDE-03-02	9- PDA2ASIDE-03-04
1.6–2.5 (0.063–0.098)	9- PDA2ASIDE-04-02	9- PDA2ASIDE-04-04
2.6–4 (0.102–0.157)	9- PDA2ASIDE-05-02	9- PDA2ASIDE-05-04

3.1.2 Device Description and Intended Indications for Use

The AMPLATZER Duct Occluder II Additional Sizes (ADO II AS) is a percutaneous transcatheter occlusion device intended for the non-surgical closure of PDAs. The AMPLATZER TorqVue LP Delivery System is intended to facilitate the attachment, loading, delivery and deployment of the ADO II AS.

The ADO II AS is a self-expandable Nitinol mesh occlusion device for the occlusion of patent ductus arteriosus (PDA). The device configuration is a central waist with two retention disks. The central waist is designed to fill the defect and the two retention disks are designed to be deployed on the arterial and venous sides of the defect. Because of the isodiametric design of the device it may be implanted in ducts longer than the device as long as the diameter of the device is sufficiently large to constrain the device within the PDA. Devices are available in three lengths to accommodate various lengths of PDA. The ADO II AS has a screw attachment for a delivery wire and radiopaque marker bands at both ends.

The AMPLATZER TorqVue LP Catheter consists of a delivery catheter, Touhy-Borst hemostasis valve, loading device, and a self-sealing hemostasis valve. The delivery catheter was designed to facilitate attachment, loading, delivery and deployment of AMPLATZER devices pre-loaded onto a delivery wire. The TorqVue LP Catheter is not investigational.

3.1.3 Device handling and storage

Sponsor requires all investigational products be stored, according to the labeling and instructions for use, in a secure area to prevent unauthorized access or use.

3.2 Device accountability

Investigational product shall be shipped to sites or approved SJM personnel after sites receive documentation of site activation and shipping authorization is complete.

The Principal Investigator or an authorized designee must maintain records of the date of receipt, the identification of each investigational device (batch number, serial number or unique code), the subject identification, the date of use, the expiration date and final disposition.

Storage locations for the devices at investigational sites will be locked with access restricted only to investigators and authorized personnel.

Sponsor must also maintain device accountability documenting all shipments and returns of investigational devices.

4 Clinical Investigation Design

4.1 Clinical Investigation Design for Pivotal IDE Subjects

The ADO II AS IDE study is a single arm, prospective, multicenter, non-randomized clinical investigation designed to characterize the safety and effectiveness of the ADO II AS device in patients with a patent ductus arteriosus (PDA). The study will be conducted at up to 10 centers within the United States.

Subjects will be implanted with the ADO II AS device using a transcatheter femoral vessel approach under fluoroscopic and echocardiographic guidance. Clinical follow-up will be performed at 1 month, 6 months, 12 months, 24 months, and 36 months following the implant procedure. A pre-market approval (PMA) application will be submitted after 40 subjects have reached 6 months of follow-up post implant attempt. A minimum of 15 subjects will be enrolled with a weight ≤ 2 kg. In the event there is difficulty in enrolling 15 subjects with a weight of ≤ 2 kg, a PMA application will be submitted after 25 subjects with weight > 2 kg have reached 6 months of follow-up. An additional submission will be done when 15 subjects with a weight of ≤ 2 kg reach 6 months of follow-up. Follow-up after 6 months will be used to satisfy the post-approval requirements. Enrollment and follow-up occurring after the PMA is submitted will be used to satisfy post-approval requirements.

[REDACTED]

[REDACTED]

4.2 Clinical Investigation Design for CAP Subjects

[REDACTED]

4.3 Objective

The objective of this clinical investigation is to characterize the safety and effectiveness of the ADO II AS device to close the ductus arteriosus in subjects with a patent ductus arteriosus (PDA).

4.4 Endpoints

The safety and effectiveness endpoints of the clinical investigation are as follows:

4.4.1 Primary Endpoints (IDE and CAP)

Primary Safety Endpoint:

The primary safety endpoint is the rate of major complications through 180 days after an attempted ADO II AS device implant (refer to Appendix B for definitions).

[REDACTED]

Primary Effectiveness Endpoint:

The primary effectiveness endpoint is the rate of effective closure of the ductus arteriosus among patients with a successful ADO II AS implant as assessed by the presence of either a Grade 0 or Grade 1 shunt, as defined below, at the six-month follow-up by transthoracic echocardiography (TTE).

PDA shunt definition:

- Grade 0—none;
- Grade 1—trivial (narrow jet adjacent to the device via the PDA). Note: the presence of flow via existing or newly formed aortopulmonary collaterals should not be considered as representing a shunt via the PDA. [REDACTED]
- Grade 2—mild (broader jet filling proximal left pulmonary artery branch and extending to main pulmonary artery);
- Grade 3/4—moderate to severe (wide jet filling the main pulmonary artery and extending to pulmonary valve or distal pulmonary artery branches, which also may be accompanied with the presence of flow reversal in the abdominal aortic Doppler pattern during diastole)

4.4.2 Secondary Endpoint (IDE and CAP)

The secondary endpoint is the rate of significant obstruction of the pulmonary artery or aorta through the 6-month follow-up visit per the following definitions:

1. Significant obstruction of the left pulmonary artery is defined as less than 30% flow to the left lung by lung perfusion scan or a peak instantaneous gradient in left pulmonary artery ≥ 35 mmHg by echocardiogram if lung perfusion scan is not available. OR
2. Significant obstruction of the aorta is defined as a gradient of ≥ 20 mmHg in the aortic isthmus by invasive aortic catheterization or a mean gradient ≥ 20 mmHg in the aortic isthmus by echocardiogram if invasive aortic catheterization is not available.

4.4.3 Descriptive Endpoints and Additional Data for Pivotal IDE Subjects

Descriptive endpoints will be reported using summary statistics.

- Implant success
- PDA shunt grade status at each follow-up visit
- Gradient measurements of the pulmonary artery and aorta at each follow-up visit
- Major and Minor Complications
- Death
- Additional data: demographics and baseline characteristics, procedure information, and left ventricular function and dimensions, pulmonic and tricuspid regurgitation, adverse events, withdrawal and protocol deviations will also be summarized at each follow-up visit.

4.4.4 Descriptive Endpoints and Additional Data for CAP Subjects

Descriptive endpoints will be reported using summary statistics.

- Implant success
- Major and Minor Complications
- Death
- Additional data: Demographics and baseline characteristics, procedure information, left ventricular function and dimensions and pulmonic and tricuspid regurgitation at 6 months, and adverse events, withdrawal and protocol deviations will also be summarized at each follow-up visit.

4.5 Study Population

The intended population for this clinical investigation is patients greater than 3 days of age with a PDA requiring closure.

4.5.1 Inclusion Criteria

To participate in this clinical investigation, the subject must meet all of the following inclusion criteria:

- Diagnosis of a PDA
- PDA \leq 4mm in diameter
- PDA \geq 3mm in length
- Subject (or legally authorized representative) is willing to comply with all pre-procedure, post-procedure, and follow-up testing requirements and provides consent to participate in the clinical study *

* This study is enrolling children and all local laws and governing IRB requirements will be followed for obtaining informed consent.

4.5.2 Exclusion Criteria

Subjects who meet any of the following exclusion criteria must be excluded from the clinical investigation:

- Weight < 700 grams at time of the procedure
- Age < 3 days at time of procedure
- Coarctation of the aorta
- Left pulmonary artery stenosis
- Cardiac output that is dependent on right to left shunt through the PDA due to pulmonary hypertension
- Intracardiac thrombus
- Active infection requiring treatment at the time of implant
- Female subjects of child bearing potential are either pregnant or desire to become pregnant within six months post implant
- Other disease process likely to limit survival to less than six (6) months
- Participating in another study for an investigational drug and/or device that may clinically interfere with this study's endpoints

5 Procedures

Approval from the Sponsor must be received prior to initiating study procedures.

Enrolled subjects (as defined in section 5.2) will undergo a PDA closure procedure with the ADO II AS device. Post-procedure, the subject will have follow-up visits at 30 days, 6 months, 12 months, 24 months, and 36 months. Subjects who do not have a successful implant will be withdrawn upon completion of the 30-day follow-up visit. Upon completion of the 36-month follow-up visit, the subject will be considered to have completed the follow-up requirements of this clinical investigation. The Principal Investigator should arrange for appropriate care of subjects following study completion.

The following sections provide a detailed description of procedures required by this CIP.

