8.2 Adverse Event Reporting

Safety surveillance within this trial (and the safety reporting performed by the investigator), starts as soon as the subject is enrolled. The safety surveillance and the safety reporting will continue until the last investigational visit has been performed, the subject is deceased, the subject/investigator concludes his/her participation into the clinical investigation or the subject withdrawal from the clinical investigation.

All adverse event data required to be reported will be collected throughout the clinical investigation and will be reported to the Sponsor on a CRF.

Adverse events will be monitored until they are adequately resolved or the subject has ended his/her participation in the trial, whichever comes first. The status of the subject's condition should be documented at each visit.

For the purposes of this clinical investigation the following events will be reported (see **Appendix B** for definitions):

- Unanticipated adverse device effects
- All adverse events viewed/interpreted by investigator to be potentially related to either a) the implant procedure or b) the study device (ADO II AS) regardless of seriousness

Note – If relatedness is unknown or cannot be determined, then the event must be reported.

Note – if a procedure is abandoned and a non-study device is used to close the PDA, adverse events associated with the non-study device will not be reported.

Records relating to the subject's subsequent medical course must be maintained and submitted (as applicable) to the Sponsor until the event has subsided or, in case of permanent impairment, until the event stabilizes and the overall clinical outcome has been ascertained. Adverse events will be monitored until they are adequately resolved. The status of the subject's condition should be documented at each visit.

SAE Reporting

Reportable adverse events that are deemed by the investigator to be serious should be reported to the Sponsor as soon as possible but no later than outlined below.

Clinical Site	Reporting timelines
All Sites	SAEs must be reported to the Sponsor no later than 3 calendar days from the day the site personnel became aware of the event or as per the investigative site's local requirements, if the requirement is more stringent than those outlined above.

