The adverse event is related to the study device/procedure – i.e. an event that follows a reasonable temporal sequence from administration of the study intervention, follows a known or expected response pattern to the suspected intervention, that is confirmed by improvement on stopping and reappearance of the event on repeated exposure and that could not be reasonably explained by the known characteristics of the subject's clinical state.

In summary, the **AE is related** to the study device (ADO II AS) or procedure if the event satisfies all of following criteria:

- Has a reasonable temporal relationship to intervention (e.g. device implant)
- Could not readily have been produced or explained by the subject's clinical state or have been due to environmental or other interventions
- Follows a known pattern of response to intervention
- Disappears or decreases with reduction in dose or cessation of intervention and recurs with re-exposure

Attempted ADO II AS Device Implant

Insertion of the TorqVue™ LP Catheter (9-TVLPC4F90/080) into the vasculature of the subject.

Major Complication

Major complications are defined as device (ADO II AS) or procedure-related adverse events resulting in any of the following:

- death,
- life-threatening adverse event,
- persistent or significant disability/incapacity, and/or
- a major open surgical intervention which is performed by a surgeon under general anesthesia

Examples of Major Complications:

- Device or procedure related events leading to death
- Cardiac perforation requiring percutaneous (e.g., pericardiocentesis) or open surgical intervention
- Cardiac tamponade
- Embolization requiring open surgical procedure (e.g., open heart surgery or femoral vessel cutdown procedure) to retrieve the device
- Persistent hemodynamic instability requiring emergency cardioversion/defibrillation therapy or emergency blood transfusion and/or institution of inotropic therapy
- Excessive blood loss or hemolysis requiring transfusion ≥ 20 cc/kg
- Persistent or worsening respiratory instability
- Cerebral or pulmonary embolism
- Persistent cardiac arrhythmia requiring a pacemaker
- Arteriovenous fistula requiring open surgical intervention
- False aneurysm of the femoral artery requiring surgical intervention
- Femoral vessel thrombophlebitis treated with intravenous antibiotics
- Infection of the device (bacterial endocarditis)

Minor Complication

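### Subjects without a successful implant leave follow-up at the 30-day visit, so 143 to 157 days of the 180-day primary safety endpoint go unobserved for each of them; the expected effect on the rate is small.

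*Combined protocol and SAP*

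**What the plan says.** Sections 4.4.1 and 6.1.1 define the endpoint for IDE and CAP alike: "The primary safety endpoint is the rate of major complications through 180 days after an attempted ADO II AS device implant". Appendix B defines the attempt as "Insertion of the TorqVue™ LP Catheter (9-TVLPC4F90/080) into the vasculature of the subject", and section 5.2 makes the same act part of the point of enrollment. Every enrolled subject thus enters the safety endpoint, implanted or not. Effectiveness, by contrast, is limited to subjects with a successful implant.

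On follow-up, the opening text of section 5 says: "Subjects who do not have a successful implant will be withdrawn upon completion of the 30-day follow-up visit". Section 5.3.3 repeats the 30-day limit for enrolled subjects with no study device in place and allows their adverse events to be collected by telephone. Table 5 puts the 1-month visit at 30 days plus or minus 7, counted from the procedure date. Under section 8.2, reporting continues only until, among other end points, the subject or investigator "concludes his/her participation into the clinical investigation or the subject withdrawal from the clinical investigation".

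Two provisions narrow what could be missed. Appendix B states: "Major complications are defined as device (ADO II AS) or procedure-related adverse events resulting in any of the following"; and an event is related "to the study device (ADO II AS) or procedure if the event satisfies all of following criteria", one of which is a reasonable temporal relationship. Section 8.2 adds that, if the procedure is abandoned and another device closes the PDA, "adverse events associated with the non-study device will not be reported".

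**The concern.** The endpoint starts its clock at the attempt and runs it for 180 days, but the follow-up rule stops observing failed attempts at about one-sixth of that time. A related major complication that first appears after withdrawal has no route into the data. Hidden analysis text after section 4.4.1 or 6.1.1.1 may say how these subjects are counted, but no counting rule can supply events that were never collected.

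Implanted subjects have no such gap. Their 6-month visit may fall as early as day 160, but surveillance continues to 36 months, so days 160 to 180 are covered later.

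What is at stake is the completeness of a primary endpoint in a small single-arm study. If subjects with about 30 days of observation are counted as event-free to day 180, any error runs towards a lower complication rate.

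**Working it through.** **Plan's own figure.** The visible text gives no expected complication rate, implant failure rate or sample-size derivation, so there is no stated figure to reproduce.

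**Inputs.** Endpoint horizon: 180 days (4.4.1, 6.1.1). Last visit for a failed implant: 30 days plus or minus 7, so day 23 to day 37 (section 5, Table 5). Both clocks start at the procedure. Section 4.1 ties the PMA submission to 40 subjects who reach 6 months after the attempt. Subjects withdrawn at 30 days cannot reach 6 months, so on that reading they come on top of the 40. The number of failures, k, is an assumption.

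**Unobserved time per subject** = 180 − day of the visit:

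- day 37: 180 − 37 = 143 days (143/180 = 79.4%)
- day 30: 180 − 30 = 150 days (150/180 = 83.3%)
- day 23: 180 − 23 = 157 days (157/180 = 87.2%)

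**Unobserved share of planned subject-days** = k × d / (N × 180), with d from 143 to 157 and all other subjects taken as observed for 180 days:

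| Failures k | Attempts N | Unobserved days / planned days | Share |
|---|---|---|---|
| 0 | 40 | 0 / 7,200 | 0% |
| 1 | 41 | 143–157 / 7,380 | 1.9–2.1% |
| 2 | 42 | 286–314 / 7,560 | 3.8–4.2% |
| 4 | 44 | 572–628 / 7,920 | 7.2–7.9% |
| 2 | 40 | 286–314 / 7,200 | 4.0–4.4% |
| 4 | 40 | 572–628 / 7,200 | 7.9–8.7% |

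The last two rows treat the 40 as attempts that include the failures. These shares describe missing observation time. They are not bias estimates, because risk need not be even over time or equal with and without a device.

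**Expected understatement of the rate** if unobserved subjects count as event-free = k × q / N, where q is the assumed chance of a first qualifying event after withdrawal. The chance of missing at least one event is 1 − (1 − q)^k. At N = 40:

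| k | q | Expected shift | Chance of at least one missed |
|---|---|---|---|
| 1 | 1% | 0.025 points | 1% |
| 2 | 5% | 0.25 points | 9.8% |
| 4 | 5% | 0.5 points | 18.5% |
| 4 | 10% | 1.0 point | 34.4% |
| 4 | 20% (extreme) | 2.0 points | 59.0% |

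**One missed event** moves the rate by 1/40 = 2.5, 1/42 = 2.4 or 1/44 = 2.3 points; among 15 subjects of 2 kg or less (the minimum in section 4.1) it is 1/15 = 6.7 points. For scale, 2/40 = 5.0% has an exact 95% interval of 0.6% to 16.9%, and 3/40 = 7.5% has one of 1.6% to 20.4%.

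**The case against.** The strongest reply is that almost nothing can be missed. An event counts only if it meets every criterion for relatedness, and one of these asks that it lessen when the intervention stops and recur on re-exposure. An event first seen more than a month after an abandoned attempt, with no study device in place, could hardly satisfy that. Events that began before withdrawal may still be followed: section 5.7 provides for subjects who withdraw because of an adverse event, and section 8.2 asks for records until an event subsides, although it elsewhere ends monitoring at the end of participation. Redacted text may define how failed attempts are evaluated. The failure counts are assumed, and one-over-N applies to any missed event from any cause. A telephone call cannot settle relatedness, which is for the Clinical Events Committee, and later treatment such as surgical ligation may confound attribution.

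Much of this stands as a limit on size. It does not remove the gap. The re-exposure criterion, read literally, is just as hard to meet for implanted subjects, while section 8.2 asks sites to report potentially related events and those of unknown relatedness. The examples in Appendix B include access-site complications that need no implanted device, such as an arteriovenous fistula or femoral false aneurysm requiring surgery, and nothing in the documents shows that these must appear before day 37. The follow-up provisions do not reach new events after withdrawal. The call only has to flag an event so that it can be adjudicated.

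**Conclusion.** The concern holds. For visits held within the window, 143 to 157 of 180 days are unobserved for each subject without a successful implant, and this follows directly from the text. That the effect on the rate is small is a judgement: with up to 4 failures in 40 attempts and a late-event chance of up to 10%, both assumed, the expected shift is at most 1 point. It may be nil. It would not be negligible if an event were in fact missed, above all among the subjects of 2 kg or less. The direction is one-sided if unobserved subjects are counted as event-free. CAP has the same gap but cannot be quantified, since its sample size is not visible. The point should be fixed because the present follow-up cannot confirm that no late related event occurred, and closing the gap takes very little.

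**What to change.** - Amend sections 5 and 5.3.3 so that reportable device- or procedure-related adverse events are collected to day 180 for every enrolled subject without a successful implant, in IDE and CAP, by telephone if needed. Place the contact on or after day 180; the 6-month window would allow day 160 and leave up to 20 days uncovered.
- Apply this to subjects enrolled or still in follow-up when the amendment takes effect. For any already withdrawn at 30 days, report their number and the days observed.
- Unless the redacted text already does so, keep all attempted implants in the safety denominator and add a sensitivity analysis that counts 0, 1, and so on up to all incompletely observed subjects as events, with exact intervals.
- Check that the wording of section 5 (successful implant) and of section 5.3.3 (study device implanted) agrees with the definition cited as section 6.1.3.2, which is not visible. A subject whose device was placed and then lost or removed could fall under one and not the other. Reconcile them only if they differ.

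The cost is one extra call for a few subjects, matching protocol and consent wording, and one short table, with no new visits or tests. Section 2.4.2 places CAP after pivotal enrollment is complete, so little may be recoverable for pivotal subjects already withdrawn; for them the remedy is disclosure.
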